[Part 3 of 4 of the document. The other parts are not shown.]

At screening, any clinically significant abnormality should be recorded as a pre-existing condition (refer to Section 10.4.1.5). During the study, any new clinically significant findings and/or abnormalities discovered on physical examination that meet the definition of an AE (or an SAE) must be recorded and document as an AE or SAE on the AE eCRF.

10.4.1.7 Hospitalization, Prolonged Hospitalization, or Surgery

Any AE that results in hospitalization or prolonged hospitalization should be documented and reported as an SAE unless specifically instructed otherwise in this protocol (refer to Section 10.2).

There are some hospitalization scenarios that do not require reporting as an SAE when there is no occurrence of an AE. These scenarios include planned hospitalizations or prolonged hospitalizations to:

- Perform a protocol-mandated efficacy measurement
- Undergo a diagnostic or elective surgical procedure for a pre-existing medical condition that has not changed
- Hospitalization solely for the purpose of insertion of an in-dwelling IV catheter (such as a Port-a-Cath or other brand) for administration of study drug will not be considered an SAE.
- Receive scheduled therapy (study drug or otherwise) for the study indication

10.4.1.8 Deaths

All deaths that occur during the AE reporting period (refer to Section 10.3.1), regardless of attribution, will be recorded on the AE eCRF and expeditiously reported to the Sponsor as an SAE.

When recording a death, the event or condition that caused or contributed to the fatal outcome should be recorded as the single medical concept on the eCRF. If the cause of death

Proprietary and Confidential

BIOMARIN	270-201 – Amendment 6	Page 68
----------	-----------------------	---------

is unknown and cannot be ascertained at the time of reporting, record "Unexplained Death" or "Death of Unknown Cause" on the AE eCRF.

10.4.1.9 Pregnancy

Although not an AE per se, pregnancy in the partner of a subject taking trial medication should be reported expeditiously to the Sponsor to facilitate outcome monitoring by the Sponsor. Pregnancy in partner should be reported during the period up to 5 years after viral infusion.

Pregnancy in a partner should be reported within 24 hours of the site becoming aware of the pregnancy by entering the information on the Pregnancy eCRF and submitting to BPV within 24 hours of the site becoming aware of the event. The Investigator must make every effort to follow the subject's partner (with that partner's consent) through resolution of the pregnancy (delivery or termination) and to report the resolution on the Pregnancy Follow-up Form in the study reference materials. In the event of pregnancy in the partner of a study subject, the Investigator should make every reasonable attempt to obtain the woman's consent for release of protected health information.

Abortion, whether therapeutic or spontaneous, should always be classified as an SAE (as the Sponsor considers these to be medically significant), recorded on the AE eCRF, and expeditiously reported to the Sponsor as an SAE.

10.5 Reporting Requirements

10.5.1 Expedited Reporting Requirements

All SAEs and EOSI that occur during the course of the AE Reporting Period (refer to Section 10.3.1), whether or not considered related to study drug, must be reported by entering the information in the AE eCRF and submitting to BPV within 24 hours of the site becoming aware of the event. Investigators should not wait to collect information that fully documents the event before notifying BPV of an SAE. BioMarin may be required to report certain SAEs to regulatory authorities within 7 calendar days of being notified about the event; therefore, it is important that Investigators submit any information requested by BioMarin as soon as it becomes available.

The Sponsor is responsible for identifying, preparing and reporting all SUSARs to the relevant competent authorities, ethics committees and investigators in accordance with the requirements identified in the Clinical Trials Regulations.

If the EDC is unavailable, all SAEs should be reported to BPV by completing the SAE Report Form and faxing or emailing the completed form to BPV within 24 hours of the site

BOMARIN	270-201 – Amendment 6	Page 69
---------	-----------------------	---------

becoming aware of the event. Once the EDC is available, the information should be entered in the AE eCRF.

10.5.2 Ethics Committee Reporting Requirements

Reporting of SAEs to the Independent Ethics Committee (IEC) will be done in compliance with the standard operating procedures and policies of the IEC and with applicable regulatory requirements. Adequate documentation must be obtained by BioMarin showing that the IEC was properly and promptly notified as required.

10.6 Follow-up of Subjects after Adverse Events

The Investigator should follow all unresolved AEs and SAEs until the events are resolved or have stabilized, the subject is lost to follow-up, or it has been determined that the study treatment or participation is not the cause of the AE/SAE. Resolution of AEs and SAEs (with dates) should be documented on the AE eCRF and submitted to BioMarin Pharmacovigilance and in the subject's medical record to facilitate source data verification.

For some SAEs, the Sponsor may follow up by telephone, fax, electronic mail, and/or a monitoring visit to obtain additional case details (eg, hospital discharge summary, consultant report, or autopsy report) deemed necessary to appropriately evaluate the SAE report.

10.7 Post-Study Adverse Events

At the last scheduled visit, the Investigator should instruct each subject to report, to the Investigator and/or to BPV directly, any subsequent SAEs that the subject's personal physician(s) believes might be related to prior study treatment.

The Investigator should notify the study Sponsor of any death or SAE occurring at any time after a subject has discontinued or terminated study participation, if the Investigator believes that the death or SAE may have been related to prior study treatment. The Sponsor should also be notified if the Investigator should become aware of the development of cancer or of a congenital anomaly in a subsequently conceived offspring of a subject that participated in this study.

10.8 Urgent Safety Measures

The regulations governing clinical trials state that the Sponsor and Investigator are required to take appropriate urgent safety measures to protect subjects against any immediate hazards that may affect the safety of subjects, and that the appropriate regulatory bodies should be notified according to their respective regulations. According to the European Union (EU) Clinical Trial Directive 2001/20/EC, "...in the light of the circumstances, notably the occurrence of any new event relating to the conduct of the trial or the development of the

Proprietary and Confidential

BIOMARIN	270-201 – Amendment 6	Page 70
----------	-----------------------	---------

investigational medicinal product where that new event is likely to affect the safety of the patients, the Sponsor and the Investigator shall take appropriate urgent safety measures to protect the patients against any immediate hazard. The Sponsor shall forthwith inform the competent authorities of those new events and the measures taken and shall ensure that the IRB/IEC/REB is notified at the same time."

The reporting period for these events which may require the implementation of urgent safety measures is the period from the time of signing of the ICF through the completion of the last study visit or at the Early Termination Visit (ETV). Investigators are required to report any events which may require the implementation of urgent safety measures to BioMarin within 24 hours.

Examples of situations that may require urgent safety measures include discovery of the following:

- Immediate need to revise the IP administration (eg, modified dose amount or frequency not defined in protocol)
- Lack of study scientific value, or detrimental study conduct or management
- Discovery that the quality or safety of the IP does not meet established safety requirements

BOMARIN	270-201 – Amendment 6	Page 71
---------	-----------------------	---------

11 APPROPRIATENESS OF MEASUREMENTS

The measures of efficacy to be used in this study are standard, ie, widely used and generally recognized as reliable, accurate, and relevant (able to discriminate between effective and ineffective agents). The measures of safety used in this study are routine clinical and laboratory procedures.

The chromogenic FXa assay and the one-stage APTT assay are both validated and utilize CE marked reagents. The exploratory FVIII activity assay will be used for exploratory purposes only.

BOMARIN	270-201 – Amendment 6	Page 73
---------	-----------------------	---------

12 STUDY PROCEDURES

12.1 Prestudy

An ICF must be signed and dated by the patient, the Investigator or designee and witness (if required) before any study-related procedures are performed.

12.2 Screening Visit

Screening assessments will be performed within 28 days (\pm 14 days) of BMN 270 infusion while baseline assessments will take place within 7 days of BMN 270 infusion (Day 1). Should the screening visit occur within 7 days of the drug infusion, physical examination, vital signs, blood chemistry, LFTs, haematology, urine tests, coagulation screen, and CRP do not need to be repeated at Baseline.

The following procedures will be performed during the Screening Period:

- Full medical history, including haemophilia A history, hepatitis B, hepatitis C, and HIV.
- Complete Physical Examination
- Height and weight
- Vital Signs (systolic and diastolic blood pressure, heart rate, respiration rate, and temperature)
- Assessment of Adverse Events and Concomitant Medications
- Documentation of bleeding episodes and FVIII usage (by either subject or clinical information)
- Electrocardiogram
- Chest X-ray
- Liver Ultrasound
- Samples for hFVIII Assays
 - Baseline hFVIII activity chromogenic FXa (plasma)
 - Baseline hFVIII activity level one-stage APTT assay
 - o hFVIII coagulation activity exploratory assay
 - o hFVIII inhibitor level (Bethesda assay with Nijmegen modification)
 - hFVIII total antibody assay
 - hFVIII antigen (ELISA)

BOMARIN [®] 270	201 – Amendment 6 Page 74
--------------------------	---------------------------

- Blood sample for AAV5 Assays
 - o AAV5 antibody titer
 - AAV5 transduction inhibition assay
- Screen for hepatitis B, hepatitis C, and HIV if required (subjects with documented negative results 30 days prior to informed consent being obtained do not need to be retested)
- Blood chemistry, haematology, coagulation screen, and CRP (refer to Table 9.7.8.2.1)
- Urine Tests (refer to Table 9.7.8.2.1)
- Liver Function Tests (refer to Table 9.7.8.3.1)
- Von Willebrand Factor Antigen (VWF:Ag)
- Blood samples for Biomarker testing (including HLA genotyping, FVIII genotyping status, TNFα and IL10a single nucleotide polymorphisms)

12.2.1 "Smart Rescreening" Visit

Subjects who undergo smart rescreening must complete the rescreening assessments and receive the infusion within 90 days of signing the original consent. Subjects who do not complete dosing within 90 days will be required to re-consent and undergo all screening procedures. Subjects may not undergo smart rescreening more than once.

If a patient has to be screened again because the original assessments have fallen out of the 28 + 14 day period allowed for Screening (refer to Section 12.2), then only the following assessments need to be performed (rather than the full list indicated in Section 12.2) for the patient to be successfully re-screened for the study:

- Vital signs
- Assessment of Adverse Events and Concomitant Medications
- Documentation of bleeding episodes and FVIII usage (by either subject or clinical information)
- hFVIII Assays (only the hFVIII inhibitor level (Bethesda assay with Nijmegen modification)
- Blood sample for AAV5 Assays
 - AAV5 antibody titer
 - AAV5 transduction inhibition assay
- Blood chemistry, haematology, coagulation screen, and CRP (refer to Table 9.7.8.2.1)

BOMARIN	270-201 – Amendment 6	Page 75
---------	-----------------------	---------

- Urine Tests (refer to Table 9.7.8.2.1)
- Liver Function Tests (refer to Table 9.7.8.3.1)

12.3 Baseline Visit

Baseline values will be recorded from 1 to 7 days prior to the treatment visit. The following procedures will be performed during the Baseline Period:

- Physical examination
- Assessment of Adverse Events and Concomitant Medications
- Documentation of bleeding episodes and FVIII usage (by either subject or clinical information)
- Distribution of subject diaries and training in diary completion
- Blood chemistry, haematology, coagulation screen, and CRP (refer to Table 9.7.8.2.1)
- Urine Tests (refer to Table 9.7.8.2.1)
- Liver Function Tests (refer to Table 9.7.8.3.1)
- PBMC collection for CTL baseline
- Direct Thrombin test
- PCR of vector DNA in blood, saliva, urine, semen, and stools
- Exploratory biomarker assessments
- Haemo-QoL-A QoL assessment

12.4 Treatment Visit/BMN 270 Infusion Visit (Day 1)

There will be one treatment visit for each subject. Subjects will remain in the clinic for 24 hours for the BMN 270 Infusion Visit. The following procedures will be performed during the BMN 270 Infusion Visit:

- Physical examination
- Assessment of Adverse Events and Concomitant Medications
- Blood sample for AAV5 Assays (must be performed before the BMN 270 infusion)
 - o AAV5 antibody titer
 - AAV5 transduction inhibition assay
- BMN 270 Infusion
- Vital Signs

BOMARIN	270-201 – Amendment 6	Page 76
---------	-----------------------	---------

Vital signs will be recorded prior to BMN 270 infusion and then every 15 minutes (± 5 minutes) during BMN 270 infusion. Following infusion, vital signs will be monitored every 1 hour (± 5 minutes) for the first 6 hours, every 2 hours (± 15 minutes) for the next 6 hours, and then at 4 hour (± 15 minutes) intervals for the remainder of the subject's stay in the clinic.

12.5 BMN 270 Infusion Follow-Up Visits

After BMN 270 has been infused, subjects will return to the study site every week $(\pm 48 \text{ hours})$ for 16 weeks, when the following procedures will be completed:

12.5.1 Once per week (Weeks 1 through 16)

The following procedures will be performed at one visit per week from Weeks 1 through 16:

- Physical examination
- Assessment of Adverse Events and Concomitant Medications (including review of subject diary for bleeding and FVIII use)
- Vital Signs
- Liver Function Tests (refer to Table 9.7.8.3.1) central laboratory assessment
 - LFTs may be monitored more or less frequently (and in particular when ALT values are >1.5x ULN) based on discussion between the Medical Monitor and the Investigator and review of subject data.
- Samples for FVIII Assays central laboratory assessment
 - FVIII activity level (one-stage APTT)
 - FVIII activity level (chromogenic FXa assay)
 - FVIII coagulation activity exploratory assay
 - o Bethesda assay (with Nijmegen modification) for hFVIII inhibitor level
 - FVIII antigen (ELISA)

Note: If a subject has used FVIII within 72 hours of a measurement day, all efforts should be made to obtain FVIII activity measurements when a 72-hour interval without FVIII use is achieved. The 72-hour wash-out period is only intended for subjects who have achieved FVIII \geq 5 IU/dL at 16 weeks after BMN 270 infusion and who have not resumed standard of care FVIII replacement therapy.

• Central assessment of FVIII activity level should be performed 1x/week from Week 1 through Week 16

BOMARIN	270-201 – Amendment 6	Page 77
---------	-----------------------	---------

- Liver Function Tests (refer to Table 9.7.8.3.1) local laboratory assessment
 - LFTs may be monitored more or less frequently (and in particular when ALT values are >1.5x ULN) based on discussion between the Medical Monitor and the Investigator and review of subject data.
- FVIII activity level local laboratory assessment
 - FVIII activity level (one-stage APTT)
 - FVIII activity level (chromogenic FXa assay)
- PBMC collection

12.5.2 Week 1 – Day 2 and Day 4

On Day 2 and Day 4 of Week 1, the following procedures will be performed:

- PCR of vector DNA in blood, saliva, urine, semen, and stools (Day 2 and Day 4)
- Samples for FVIII Assays (Day 4 only) central laboratory assessment
 - FVIII activity level (one-stage APTT)
 - FVIII activity level (chromogenic FXa assay)
 - FVIII coagulation activity exploratory assay
 - Bethesda assay (with Nijmegen modification) for hFVIII inhibitor level
 - FVIII antigen (ELISA)

Note: If a subject has used FVIII within 72 hours of a measurement day, all efforts should be made to obtain FVIII activity measurements when a 72-hour interval without FVIII use is achieved. The 72-hour wash-out period is only intended for subjects who have achieved FVIII \geq 5 IU/dL at 16 weeks after BMN 270 infusion and who have not resumed standard of care FVIII replacement therapy.

- Liver Function Tests (refer to Table 9.7.8.3.1) (Day 4 only) central laboratory assessment
- Liver Function Tests (refer to Table 9.7.8.3.1) (Day 4 only) local laboratory assessment
- FVIII activity level (Day 4 only) local laboratory assessment
 - FVIII activity level (one-stage APTT)
 - FVIII activity level (chromogenic FXa assay)

12.5.3 Week 1 – Day 8

On Day 8, the following procedures will be performed:

• PCR of vector DNA in blood, saliva, urine, semen, and stools

BOMARIN	270-201 – Amendment 6	Page 78
---------	-----------------------	---------

- Direct Thrombin test
- Haemo-QoL-A QoL assessment

12.5.4 Every 2 Weeks

Every 2 weeks (Weeks 2, 4, 6, 8, 10, 12, 14 and 16), the following procedures will be performed:

- Blood chemistry, haematology, coagulation screen, and CRP (refer to Table 9.7.8.2.1) (not assessed at Week 14)
- PCR of vector DNA in blood, saliva, urine, semen, and stools (not collected at Week 2)
 - Collection to occur until at least 3 consecutive negative results are obtained. Semen samples should continue to be collected and tested through Week 12, even if 3 consecutive negative results in that compartment have been recorded prior to that timepoint.

12.5.5 Weeks 4, 8, 12, and 16

At Weeks 4, 8, 12, and 16, the following procedures will be performed:

- Urine Tests (refer to Table 9.7.8.2.1)
- VWF:Ag
- FVIII antibody titer
- Exploratory biomarker assessments

12.5.6 Week 16

At Week 16, the following procedures will be performed:

- Test for hepatitis B and hepatitis C reactivation (in subjects with a history of hepatitis B or hepatitis C infection prior to study entry)
 - Subjects who receive therapeutic corticosteroids prior to Week 16 do not need to complete the Week 16 reactivation assessment; instead, they will be tested for hepatitis B and hepatitis C reactivation at the time points listed in Table 9.1.5.

12.5.7 Weeks 8 and 16

At Weeks 8 and 16, the following procedures will be performed:

• AAV5 antibody titer

12.5.8 Weeks 2, 3, 4, and 16

At Weeks 2, 3, 4, and 16, the following procedure will be performed:

Proprietary and Confidential

BOMARIN	270-201 – Amendment 6	Page 79
---------	-----------------------	---------

• Haemo-QoL-A QoL assessment

12.5.9 Week 13

At Week 13, the following procedure will be performed:

• Direct Thrombin test

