12.6.4 Every 4 Weeks

Every 4 weeks (Weeks 20, 24, 28, 32, and 36), the following procedures will be performed:

- Exploratory biomarker assessments
- Blood chemistry, haematology, coagulation screen, and CRP (refer to Table 9.7.8.2.1)
- Urine Tests (refer to Table 9.7.8.2.1)
- VWF:Ag
- AAV5 antibody titer
- PCR of vector DNA in blood, saliva, urine, semen, and stools
 - Sample testing during Safety Follow-Up is not required if at least
 3 consecutive samples are clear during the Post-Infusion Follow-Up period.

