12.7.2 Every 4 Weeks

Every 4 weeks (Weeks 40, 44, 48, and 52), the following procedures will be performed:

- Exploratory biomarker assessments
- Blood chemistry, haematology, coagulation screen, and CRP (refer to Table 9.7.8.2.1)
- Urine Tests (refer to Table 9.7.8.2.1)
- AAV5 antibody titer
- VWF:Ag
- PCR of vector DNA in blood, saliva, urine, semen, and stools
 - Sample testing during Safety Follow-Up is not required if at least 3 consecutive samples are clear during the Post-Infusion Follow-Up period. Subjects who have not had 3 consecutive negative samples by Week 52 should continue to have PCR testing every 4 weeks until 3 consecutive negative samples are documented (or upon consultation between the Investigator and Medical Monitor).

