12.8.5 Years 2-5 – Every 4 Weeks

Every four weeks during Years 2-5, the following procedure may be performed:

- PCR of vector DNA in blood, saliva, urine, semen, and stools
 - Sample testing during Years 2-5 is not required if at least 3 consecutive samples are clear during the Post-Infusion Follow-Up period. Subjects who have not had 3 consecutive negative samples by Week 52 should continue to have PCR testing every 4 weeks during Years 2-5 until 3 consecutive negative samples are documented (or upon consultation between the Investigator and Medical Monitor).

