12.9 Early Termination Visit

The Early Termination visit will occur on the date the subject withdraws from the study, even if the date does not correspond to a protocol-specific visit.

If a subject leaves the study prior to the Week 260 visit, the subject will be asked to return to the study site and complete an Early Termination visit. At the Early Termination visit, as many of the following assessments as possible should be done:

• Physical examination

BOMARIN	270-201 – Amendment 6	Page 86
---------	-----------------------	---------

- Assessment of Adverse Events and Concomitant Medications (including review of subject diary for bleeding and FVIII use)
- Vital Signs
- Blood chemistry, haematology, coagulation screen, and CRP (refer to Table 9.7.8.2.1)
- Urine Tests (refer to Table 9.7.8.2.1)
- Liver Function Tests (refer to Table 9.7.8.3.1) local laboratory assessment
- FVIII activity level local laboratory assessment
 - FVIII activity level (one-stage APTT)
 - FVIII activity level (chromogenic FXa assay)
- Liver Function Tests (refer to Table 9.7.8.3.1) central laboratory assessment
- FVIII Assays central laboratory assessment
 - FVIII activity level (one-stage APTT)
 - FVIII activity level (chromogenic FXa assay)
 - FVIII coagulation activity exploratory assay
 - o Bethesda assay (with Nijmegen modification) for FVIII inhibitor level
 - FVIII antigen (ELISA)

Note: If a subject has used FVIII within 72 hours of a measurement day, all efforts should be made to obtain FVIII activity measurements when a 72-hour interval without FVIII use is achieved; the 72-hour wash-out period is only intended for subjects who have achieved FVIII \geq 5 IU/dL at 16 weeks after BMN 270 infusion and who have not resumed standard of care FVIII replacement therapy.

- AAV5 antibody titer
- FVIII antibody titer
- PBMC collection
- VWF:Ag
- Direct Thrombin test
- PCR of vector DNA in blood, saliva, urine, semen, and stools
 - Sample testing at the ETV is not required if at least 3 consecutive samples are clear during the Post-Infusion Follow-Up period.
- Exploratory biomarker assessment
- Haemo-QoL-A QOL assessment

BOMARIN	270-201 – Amendment 6	Page 87
---------	-----------------------	---------

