Rationale: Previous FIX gene-therapy clinical studies have demonstrated an association between increases in ALT and declines in FIX expression, which are thought to be due to a cell-mediated immune response to transduced hepatocytes (Manno, 2006, Nat.Med.) (Mingozzi, 2013, Blood); (Nathwani, 2014, N.Engl.J.Med.); (Nathwani, 2011, Mol.Ther.). An analysis of this immune response requires the collection of peripheral blood mononuclear cells (PBMC), which is part of the current schedule of assessments. The transient nature of the reported data indicates we may need to sample more frequently to identify a potential cell-mediated immune response to transduced hepatocytes. The frequency of PBMC collection has been increased from every 4 weeks to weekly through Week 20, then to every 2 weeks through Week 36.

BOMARIN	270-201 – Amendment 5	Page 3
---------	-----------------------	--------

3. Subjects will be required to continue to provide semen samples for PCR analysis through Week 12, even if they have already had 3 consecutive negative results in semen prior to that timepoint.

Rationale: A monitoring period of at least 12 weeks is required for semen to conform with regulatory guidances for shedding analysis, which recommend monitoring for at least one complete cycle of spermatogenesis (mean: 74 days, 95% CI interval: 70-78 days) (Heller and Clermont, 1964; Heller, 1969). Collection and testing of semen for vector DNA will therefore be continued through Week 12, regardless of whether the semen fluid compartment is considered to have cleared (i.e., the subject has had 3 consecutive negative sample tests). This new minimal monitoring period should account for the potentially delayed appearance of vector DNA in semen if a sperm progenitor cell had been transduced.

4. Language has been added to allow exploratory fractionation of collected samples (such as plasma, PBMCs, and red blood cells).

Rationale: On an exploratory basis, samples may be fractionated prior to shedding analysis in order to better characterize the presence and location of vector DNA and/or vector capsid within each matrix. The fractionation may be performed with a portion of samples designated for shedding analysis (saliva, blood, semen, urine, faeces), or by using exploratory samples, such as plasma, PBMCs, and red blood cells, collected under the study protocol.

5. Minor administrative changes have been made for consistency and clarity.

[figure not shown]

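### Three consecutive negative semen samples waive all later semen PCR, even if a mandatory Week 10 or Week 12 sample taken after them is positive

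*Protocol*

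**What the plan says.** Section 12.5.4 (Amendment 6) gives the general stopping rule for shedding samples: "Collection to occur until at least 3 consecutive negative results are obtained". For semen it adds a minimum period: "Semen samples should continue to be collected and tested through Week 12, even if 3 consecutive negative results in that compartment have been recorded".

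The later sections waive PCR on one common condition:

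- Section 12.7.2 (Weeks 40 to 52): "Sample testing during Safety Follow-Up is not required if at least 3 consecutive samples are clear during the Post-Infusion Follow-Up period". Section 12.6.4 (Weeks 20 to 36) sets the same condition.
- Section 12.8.5: "Sample testing during Years 2-5 is not required if at least 3 consecutive samples are clear during the Post-Infusion Follow-Up period".
- Section 12.9: "Sample testing at the ETV is not required if at least 3 consecutive samples are clear during the Post-Infusion Follow-Up period".

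Sections 12.7.2 and 12.8.5 also carry a continuation rule. In 12.7.2 it reads: "Subjects who have not had 3 consecutive negative samples by Week 52 should continue to have PCR testing every 4 weeks".

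The semen floor came in with Amendment 5. Item 3 of that amendment's summary of major changes links it to one cycle of spermatogenesis (mean 74 days, interval 70 to 78) and gives its purpose: "This new minimal monitoring period should account for the potentially delayed appearance of vector DNA in semen".

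**The concern.** For a man who already has three negatives, the floor samples have one use: to show whether vector DNA turns up late. The protocol collects them but attaches no consequence to a positive. The waiver asks only whether a clear run occurred at some point in Post-Infusion Follow-Up, and an early run meets that condition whatever follows.

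Three things depend on this:

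- **Follow-up to clearance.** The positive is sampled and reported, but repeat testing until it clears is not required.
- **Contraception.** Section 9.3.1, criterion 6, and Section 9.7.8.6 make three consecutive negative semen samples the condition for stopping after 6 months. Read literally, the run before the positive meets it.
- **The enrolment-halt criterion on semen.** Section 9.3.3.1 needs three consecutive positive semen samples more than 52 weeks after infusion. A waived subject has no required sampling that could supply them.

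**Working it through.** The protocol gives no figure to reproduce. The check applies its rules literally to the sampling schedule.

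**Inputs**

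- Semen PCR visits from Week 4: Weeks 4, 6, 8, 10, 12, 14 and 16 (12.5.4), then 20, 24, 28 and 4-weekly (12.6.4, 12.7.2).
- Semen floor: Week 12 (12.5.4).
- Contraception minimum: 6 months, or 26 weeks (9.3.1, 9.7.8.6).
- Earliest plausible clearance: Amendment 4, rationale item 4, reports that the first fluid to clear was urine, and not before Week 4. Runs built on Day 2, 4 or 8 samples are therefore set aside.

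**Step 1: what the floor adds.** If the run ends at Week 8, the floor adds Weeks 10 and 12 (two samples). If it ends at Week 10, it adds Week 12 (one sample). Weeks 10 and 12 are Days 10 × 7 = 70 and 12 × 7 = 84, either side of the 74-day mean cycle.

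**Step 2: patterns that fall in the gap.** Over Weeks 4 to 12 only two negative runs can be complete before a mandatory later sample: Weeks 4-6-8 and Weeks 6-8-10. Followed by a positive in the floor samples, they give four patterns:

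| W4 | W6 | W8 | W10 | W12 | Required semen PCRs after the last positive, as written | Minimum if a positive resets the count |
|---|---|---|---|---|---|---|
| − | − | − | + | − | 1 (Week 12) | 3 (Weeks 12, 14, 16) |
| − | − | − | − | + | 0 | 3 (Weeks 14, 16, 20) |
| − | − | − | + | + | 0 | 3 (Weeks 14, 16, 20) |
| + | − | − | − | + | 0 | 3 (Weeks 14, 16, 20) |

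These are possible result patterns, not probabilities.

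**Step 3: does another rule catch these subjects?** The continuation rule in 12.7.2 and 12.8.5 covers only subjects who have not had three consecutive negatives by Week 52, and all four have. The consultation clause attached to it offers a way to end extended testing, not to restart it. Section 9.7.8.6 says contraception may need extending on observed semen shedding, but it does not restore PCR.

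**Step 4: does three consecutive negatives plainly mean the latest three?** No. Item 3 of the Amendment 5 summary treats semen as cleared once the subject has had three consecutive negative tests. That is a past event with no reset.

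**Step 5: timing under a reset.** After a Week 10 positive, the earliest clearance is Week 16, which is 26 − 16 = 10 weeks before the contraception minimum. After a Week 12 positive it is Week 20, which is 26 − 20 = 6 weeks before it.

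**The case against.** The strongest reply is that the gap is small, unlikely and partly covered.

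- **Few subjects are exposed.** Nine had been dosed by Amendment 4 (2 September 2016). The floor arrived with Amendment 5 (14 February 2017), 165 days or 165 / 7 = 23.6 weeks later, so all nine were past Week 16. With a cap of 15, at most 15 − 9 = 6 men can have floor samples. This stands, and it bounds the problem.
- **The pattern runs against the trial's data.** Amendment 4 (items 4 and 6) describes slow clearance in most fluids, declining semen levels and semen expected to clear by Week 40. This also stands as a reason to think the pattern uncommon.
- **The one observed return does not show the rule failing.** A subject was semen-positive at Week 28 after two negatives. He was one short of the stop count, so testing continued and found it. That is correct. The case shows only that detection can return after negatives in this trial.
- **Discretion remains.** Waived testing is not forbidden testing. The contraception wording states a necessary condition, not automatic release. The medical monitor and Data Review Board review individual data. All true, but each leaves the response to a late positive to judgment that can differ between sites.
- **The text is silent rather than wrong.** This does not stand. The waiver is an express rule, and on its own terms it releases a subject with a Week 12 positive.

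**Conclusion.** The concern holds. Followed literally, the protocol requires no semen PCR after a Week 12 positive that follows three negatives, and one after a Week 10 positive. That is the delayed-appearance case the floor exists to detect. The documents give no rate for it. The clearance data suggest it is low, and at most six subjects are exposed. Because this is a safeguard against germline exposure and the correction is cheap, the wording should be changed.

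Two assumptions apply. The restriction to two negative runs assumes semen does not clear before Week 4; without it, earlier runs would qualify too. The Section 9 text cited here is from Amendment 5, because Section 9 of Amendment 6 is not in the part available. The Amendment 6 revision table (Section 24) lists no change to 9.3.1, 9.3.3.1 or 9.7.8.6.

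**What to change.** Define semen clearance once: the most recent three consecutive semen results are negative, and the last of them was taken at or after Week 12. Any later positive resets the count, and sampling resumes on the existing schedule (Weeks 14 and 16, then 4-weekly). State that the new run may finish in Safety Follow-Up.

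Use this definition wherever the three-negative condition applies to semen: stopping collection (12.5.4); the waivers in 12.6.4, 12.7.2, 12.8.5 and 12.9; the Week 52 continuation rule; and release from contraception after 6 months (9.3.1, 9.7.8.6).

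The cost is protocol wording. A subject negative at Weeks 8, 10 and 12 needs no extra test. A Week 10 positive followed by a negative at Week 12 adds at least two PCRs (Weeks 14 and 16), and a Week 12 positive adds at least three (Weeks 14, 16 and 20), all at visits already scheduled. A subject who clears at once does so before Week 26, so his contraception period is not lengthened.
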